**- Methodology in details:**

- Patients will present to the outpatient clinic of KASR ALAINY hospitals with pancreatic head tumours, cholangiocarcinoma, duodenal tumours (1st, 2nd and 3rd part) and ampullary tumours who are fit for either open or laparoscopic pancreaticoduodenectomy.
- Full assessment will be done by clinical examination, radiological assessment in the form of EUS, CT scan and metastatic work-up, laboratory investigations in the form of tumour markers and tissue biopsy histopathological examination.
- Patients will be classified into frank resectable, borderline resectable (defined as pancreatic head masses larger than 4 cm in size, equivocal findings of ascites and metastases on CT scan and signs of advanced disease as in marked weight loss and markedly elevated CA19-9 > 1000) and frank irresectable.
- A decision will be made by the multidisciplinary team and patients will be selected to undergo total laparoscopic pancreaticoduodenectomy or open pancreaticoduodenectomy through a randomized manner
- Patients with tumours classified as borderline resectable tumours will be subjected to diagnostic laparoscopy prior to open surgery
- A diagnostic survey and intraoperative ultrasonography were performed to assess for resectability and other pathological conditions such as the presence of ascites, liver metastases and peritoneal deposits and a decision to proceed or abort will be made accordingly.
- Patients classified as borderline resectable will undergo an intraoperative ultrasound assessment of the vessel involvement, LNs and tumour size if irresectability is suspected.
- Open approach will entail a roof top incision
- Laparoscopic approach will entail trocar placement at the following sites:
  - 10 mm visual port at the level of the umbilicus
  - 12 mm port in the right mid-clavicular line 2 cm below the umbilicus
  - 5 mm port in the left mid-clavicular line 2 cm below the umbilicus
  - 5 mm port in the right mid-clavicular line 2 cm above the umbilicus
  - 5 mm port in the left mid-clavicular line 2 cm above the umbilicus
  - An optional 5mm port in the epigastric region if required
- Total internal stents will be placed inside the pancreatic and biliary anastomoses. The size of the stents will be determined according to caliber of pancreatic duct and common bile duct.
- Operative time will be calculated in minutes starting from skin incision to skin closure

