**9- Study outcomes:**

- **Primary outcome:**

- o Operative time
- o Assessment of early post-operative complications including: pain, respiratory complications (collapse, pleural effusion or pneumonia)
- o Incidence of pancreatic and biliary leakage

- **Secondary outcome:**

- o ICU stay and total hospital stay
- o Patient satisfaction in terms of pain, ambulation, ability to resume daily routine activities
- o Blood loss and need for blood transfusion accordingly

- Wound complications including: infection (early) and incisional hernia/port site hernia (late)
- Pathological assessment in terms of LN harvesting and resection margins (R0 resection or R1)

---

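### Borderline patients appear to be randomised before the operative staging that decides whether resection goes ahead; their allocation should be opened only after that decision

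*Combined protocol and SAP*

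**What the plan says.** The detailed methodology in Section 6 is a bullet list. After imaging, laboratory work-up and biopsy, patients are classed as resectable, borderline or irresectable. The borderline class includes patients with "equivocal findings of ascites and metastases on CT scan". The multidisciplinary team then decides, and "patients will be selected to undergo total laparoscopic pancreaticoduodenectomy or open pancreaticoduodenectomy through a randomized manner".

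Operative staging is listed only after that:
- For the borderline class: "Patients with tumours classified as borderline resectable tumours will be subjected to diagnostic laparoscopy prior to open surgery".
- A survey with intraoperative ultrasonography, naming no arm, after which "a decision to proceed or abort will be made accordingly".
- A further ultrasound for borderline patients when irresectability is suspected, again naming no arm.

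The approaches follow: "Open approach will entail a roof top incision" and "Laparoscopic approach will entail trocar placement at the following sites". The clock is defined once: "Operative time will be calculated in minutes starting from skin incision to skin closure".

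The exclusion criteria in Section 6 remove metastatic and irresectable disease without saying at which stage of the work-up. Section 9 makes operative time a primary outcome, together with "Incidence of pancreatic and biliary leakage". Section 10 plans 12 patients per group. Section 11, on statistical analysis, has a heading but no text in the document supplied, so no rule for a randomised patient whose resection is abandoned can be found there.

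**The concern.** Randomisation protects the comparison only if what happens after it does not select patients differently by arm. A surgeon who must decide whether to go on with a borderline tumour, and who knows whether the resection will be open or laparoscopic, may set a different threshold in each arm. Aborts, or exclusions as irresectable, could then differ between arms for reasons other than disease.

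Two primary outcomes are exposed. An aborted patient has a short operation and no anastomosis, so cannot leak. Keeping such patients lowers operative time and leakage in that arm. Dropping them leaves two groups that are no longer the randomised ones. With 12 per arm, a single patient is visible in the result.

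A smaller, related question is the clock. A borderline patient in the open arm may have two incisions that could start it: the laparoscopy port and the later roof top incision. The plan does not say which one counts.

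**Working it through.** **The plan's own figure.** Section 10 gives hospital stays of 4.7 (SD 1.125) and 8.9 (SD 5.425) days, 80% power and alpha 0.05. The difference is 8.9 - 4.7 = 4.2 days. The pooled SD is sqrt((1.125² + 5.425²)/2) = 3.918, so d = 4.2/3.918 = 1.072. A one-sided t-test needs 11.50, so 12 per group, which matches the plan. A two-sided t-test needs 14.68, so 15. Sidedness is not stated. No allowance for aborted resections is mentioned. Here the 12 serves only as the denominator.

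**Order of events, from the text.**
1. Random selection sits with the multidisciplinary decision, before any operative staging bullet.
2. The borderline laparoscopy is worded by arm. Staging that is specific to open surgery presupposes that the arm is known.
3. The proceed-or-abort decision rests on operative findings, so it comes after the laparoscopy or ultrasound.
4. Nothing places allocation after that decision.

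The most natural reading is therefore randomise, stage, then decide.

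**How often an abort could occur.** The documents give no rates. Assume a borderline share b of 0.20 to 0.50, an abort share a among borderline patients of 0.10 to 0.40, and independent patients.
- Borderline patients per arm, 12b: 2.4 to 6.
- Abort share of all patients, p = b × a: 0.20 × 0.10 = 0.02 to 0.50 × 0.40 = 0.20.
- Expected aborts per arm, 12p: 0.24 to 2.4.
- Chance of at least one among 24, 1 - (1 - p)^24: 1 - 0.98^24 = 0.384 to 1 - 0.80^24 = 0.995.

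**What one abort does in an arm of 12.**
- Share of the arm: 1/12 = 8.3%.
- Leakage, with two leaks: 2/12 = 16.7% if the abort is kept, 2/11 = 18.2% if dropped, a difference of 1.5 points.
- Operative time: if an aborted case is 150 to 300 minutes shorter than a resection (assumed), keeping it lowers the arm mean by 150/12 = 12.5 to 300/12 = 25 minutes.
- If aborted patients are dropped at the upper share of 20%, 12 per arm leaves 12 × 0.80 = 9.6, and 12/0.80 = 15 would have to be randomised to keep 12.

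**The clock.** Assume a staging laparoscopy takes D = 20 to 45 minutes. Counting it or leaving it out moves the open-arm mean by b × D: 0.20 × 20 = 4 minutes to 0.50 × 45 = 22.5 minutes. This becomes a difference between arms only if the open-arm clock restarts at the roof top incision, or if the laparoscopy is a separate, untimed session. The documents say neither.

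**What these figures do not show.** The abort expectation is the same in both arms unless knowledge of the arm changes decisions. The figures show that aborts are plausible and that one matters. They do not size a between-arm bias. The documents give no mean or SD for operative time against which to judge the minutes.

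**The case against.** The strongest reply is that the sequence is inferred. The list carries no dates, mixes past and future tense, and does not rule out allocation after staging. That stands: the timing is the most natural reading, not a demonstrated fact. It does not remove the point, because laparoscopy worded by arm makes sense only if the arm is already known, and no text says otherwise.

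A second reply is that the exclusion criteria make a patient found irresectable at staging ineligible, so such a patient would never appear as a short operation without a leak. The criteria do not say when they apply. If they apply after randomisation, they become exclusion with the arm known, which is the same problem in another form.

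A reader might go further and infer that laparoscopic-arm patients are staged less carefully. The documents do not support this. The survey and both ultrasound provisions name no arm, and a laparoscopic resection starts with a visual port anyway. The open-arm laparoscopy may simply supply what the other arm already has.

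A reader might also infer that operative time is already biased by the minutes above. That too goes beyond the text. Skin incision most naturally means the first incision, and for a same-session laparoscopy that is the port, so staging would count in both arms.

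Finally, allocation in theatre is a real burden for an unfunded study of 24 patients. That stands as a cost.

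**Conclusion.** The point holds in a limited form. As written, the plan allows borderline patients to be randomised before the step that decides whether they are resected, so they can be aborted or excluded with the arm known. This rests on the most natural reading of the list and is not proved by it. Unequal staging between arms and a biased clock are not shown.

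The size of any bias is unknown. One abort is 8.3% of an arm, and under the assumed ranges at least one abort among 24 is anywhere from fairly likely (38%) to almost certain (over 99%). The effect on leakage is small per patient. At the low end of the assumptions the whole effect is small. The change is still worth making, because a specific and better order is available at modest cost. The clock and the reporting of aborts, taken alone, would be little more than missing detail.

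**What to change.** 1. Give every borderline patient the same staging laparoscopy before allocation, with ultrasound if irresectability is suspected.
2. Open the allocation for these patients only after the decision to proceed, so that anyone aborted at staging is never randomised. Frankly resectable patients can be allocated before surgery as now. State that the exclusions for metastatic and irresectable disease apply up to allocation and not after it.
3. Use one clock rule in both arms. As the primary measure, start at the first skin incision of the resection session, staging ports included. If staging is in a separate session, leave it out of the clock in both arms.
4. If any patient, including a frankly resectable one, is aborted after randomisation, keep that patient in the allocated arm, report aborts by arm, and add a sensitivity analysis in completed resections.

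**Cost.** Both operative set-ups must be ready for borderline cases, and consent must cover allocation in theatre, which makes list planning harder. There is little extra surgery: open-arm borderline patients already have the laparoscopy, and laparoscopic-arm patients need ports anyway. The operative form gains two or three fields: time of first incision, time of the decision to proceed, and whether the resection was aborted. If allocation in theatre cannot be managed, the fallback is the same staging rule in both arms with items 3 and 4. That is cheaper, but it leaves the abort decision open to knowledge of the arm.

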#### 4. Background and Rationale:

Total laparoscopic pancreaticoduodenectomy (TLPD) remains one of the most advanced laparoscopic procedures. Owing to the evolution in laparoscopic technology and instrumentation within the past decade, laparoscopic pancreaticoduodenectomy is beginning to gain wider acceptance.(1)

Gagner and Pomp were the first to describe the laparoscopic Whipple procedure in 1994. The long operative times and technical difficulties coupled with the need to develop advanced laparoscopic skills were valid reasons that supported the initial reluctance to pursue these sophisticated minimally invasive operations. Recently, laparoscopic pancreaticoduodenectomy has started to gain wider acceptance as surgeons become more comfortable with laparoscopic technology. As a result, TLPDs have been reported with an increased frequency from institutions internationally.(2-15)

In recent years, total laparoscopic pancreaticoduodenectomy (TLPD) has been introduced as a feasible alternative to open pancreaticoduodenectomy (OPD) when performed by experienced surgeons in laparoscopic and pancreatic surgery. Its application has been gradually increased, but its safety, reproducibility, and oncological outcomes are still debated due to its technical complexity and prolonged operating time. There are different experiences present in the literature regarding indications, surgical techniques, postoperative outcomes, benefits and limitations of this approach, oncological results, learning curve, and costs. There is no standardized surgical technique for TLPD. Different techniques exist for both the demolitive stage and the reconstructive stage. We summarized the different aspects of the surgical technique based on the various experiences reported by different authors. Compared to OPD, TLPD provides the advantages of laparoscopy, i.e., reduced blood loss, decreased postoperative pain, and shorter length of hospital stay, without increasing the rate of postoperative complications or compromising oncological outcomes. With increased experience, more challenging cases may also be approached with this technique, including those requiring major vascular resections or multi-visceral resections.(16)

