- Blood loss will be assessed in coordination with the anaesthesia team by counting the number of soaked towels and gauze and calculating the amount of blood suctioned throughout the procedure.
- Daily chest assessment to exclude or suspect lung atelectasis, pleural effusion or pneumonia will be done. Further chest imaging will be done if required.
- Daily serial abdominal examination to exclude or suspect pancreatic or biliary leakage will be done. Further laboratory assessment will be done if required (inflammatory markers: TLC, CRP, serum and drain amylase, serum and drain bilirubin), imaging in the form of an abdomen and pelvis CT study may be done if required.
- Daily wound assessment will be done starting 48 hours following surgery
- Pain assessment will be done by means of a visual analogue scale (VAS)
- Early patient satisfaction in terms of post-operative pain, early ambulation, ability to resume daily activities and complications by means of a questionnaire
- ICU stay and total hospital stay will be calculated
- Pathological assessment will be noted in terms of number of LNs harvested and the resection margins (R0 or R1)
- Incision / portsite examination to exclude incisional or portsite hernia.

○ **Does the research involve?**

Human participants

Biological samples/Tissues

Identifiable private data/Information

○ **Type of consent of study participants:**

Written consent

Oral consent

Cairo University

KASR ALAINY  
CAIRO UNIVERSITY - FACULTY OF MEDICINE

No consent needed (Please justify)

o **Potential risks:**

No attributed risks can be related to the study

o **Confidentiality of data:**

All study related information will be stored securely at the study site.

All participant information will be stored in locked file cabinets in areas with limited access.

Participants' study information will not be released outside the study without the written permission of the participant.

Research ethics committee "REC" & Health authorities have the right to review's patient's data

---

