#### 10- Sample size

The sample size was assessed using the G \* power 3.1.9.4 software (Universities Kiel, Germany). The calculation was based on the study of Ammori et al. [11], which reported a mean hospital stay length of  $4.7 \pm 1.125$  days in the OPD group compared to a respective mean of  $8.9 \pm 5.425$  days in the LPD group. After setting the study power at 80% and  $\alpha$  at 0.05, a minimum of 12 patients in each group were required.

---

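### Blood loss is measured by counting soaked towels and adding suction, which leaves the open-versus-laparoscopic comparison exposed to measurement error that may differ by arm

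*Combined protocol and SAP*

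**What the plan says.** Section 6 (Methodology in details) gives the whole method in one sentence. The volume is to come from "counting the number of soaked towels and gauze and calculating the amount of blood suctioned throughout the procedure", and the anaesthetists share in the assessment. The same rule applies to both arms. The section gives no volume per towel or gauze, no definition of soaked, no weighing, no step for handling irrigation fluid, and no assessor independent of the theatre team.

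Section 9 lists the result as a secondary outcome: "Blood loss and need for blood transfusion accordingly". Section 4 summarises the literature as showing three advantages for the laparoscopic approach: "reduced blood loss, decreased postoperative pain, and shorter length of hospital stay".

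The two arms differ in access. Section 6 says "Open approach will entail a roof top incision". The laparoscopic arm uses ports of 5 to 12 mm, the largest being the "12 mm port in the right mid-clavicular line 2 cm below the umbilicus".

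Section 11 (Statistical analysis) is a heading without text, so no analysis of blood loss is specified that might deal with measurement error.

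**The concern.** Using the same rule in both arms protects a comparison only if the rule's average error is the same in both arms. This rule has two parts with different sources of error. The towel part depends on a volume per towel that nobody has written down, and on a judgement of what counts as soaked. The suction part depends on how blood is separated from other fluid. If the surgical approach changes how much of the loss falls in each part, it also changes the error. Randomization balances patients; it does not balance an error that follows from the assigned operation. A larger sample would not remove such an error either.

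What is at stake is the attribution of any blood loss difference to the approach. Readers will look for this result because the Background names it as a benefit of laparoscopy. Section 9 also ties transfusion need to blood loss, so an error in the first may carry into the second.

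**Working it through.** **The plan's own figures.** The documents give no blood loss, no volume per towel and no measurement error, so there is no figure on this point to reproduce. The only calculated figure is the sample size: alpha is set "at 0.05, a minimum of 12 patients in each group were required". It is based on hospital stay: difference 8.9 − 4.7 = 4.2 days, pooled SD √((1.125² + 5.425²)/2) = 3.918, standardized difference 1.072. A one-sided t test at 0.05 then gives 12 per group (power 81.6%). Blood loss plays no part in it. It is used below only for the number of operations, 2 × 12 = 24.

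**Step 1: does access change the mix?** Section 6 gives one arm a wide incision and the other ports of at most 12 mm. Full-size towels are hardly usable through such ports. It is therefore likely that more of the open total comes from towels and more of the laparoscopic total from suction. This is an inference from the access described; the documents do not give the split.

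**Step 2: a fixed error per towel.** Let e be the assumed minus the true volume per towel, and k the number of towels.

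- Error in an arm = k × e
- Difference between arms = (k open − k laparoscopic) × e

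All values here are assumptions. If 100 mL is credited per towel and the true volume is 60 to 140 mL, e lies between −40 and +40 mL. With 10 open and 2 laparoscopic towels at the extreme, the errors are 10 × 40 = 400 mL and 2 × 40 = 80 mL, and the difference is 320 mL. Over a range (the sign follows the sign of e):

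| Difference in towel count | e = 10 mL | e = 20 mL | e = 40 mL |
|---|---|---|---|
| 0 | 0 | 0 | 0 |
| 4 | 40 mL | 80 mL | 160 mL |
| 8 | 80 mL | 160 mL | 320 mL |

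**Step 3: random error per towel.** If towel errors were instead independent and uniform over ±40 mL, the SD per towel would be 80/√12 = 23 mL. For a 10-towel case it would be 23.1 × √10 = 73 mL, and for the mean of 12 such cases 73/√12 = 21 mL, centred on zero. That is noise, not bias. Only a systematic error, as in Step 2, shifts the comparison.

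**Step 4: irrigation.** Each 500 mL (an assumed amount) left in the suction reading adds 500 mL in whichever arm it occurs. The difference between arms is the difference in unsubtracted irrigation, which is zero if the amounts are equal. The documents give no irrigation volumes for either arm.

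**Step 5: what a shift would do to a test.** Assume no true difference, 12 per group, a two-sided t test at 0.05 (22 degrees of freedom) and a coefficient of variation (CV) of blood loss of 0.4 to 0.8. If average error differs between arms by a fraction δ of mean loss, the shift is δ/CV in SD units and the noncentrality is (δ/CV) × √(12/2).

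| δ | Shift (SD) | False-positive rate |
|---|---|---|
| 0 | 0 | 5% |
| 5% | 0.06–0.13 | 5.2–6.0% |
| 10% | 0.13–0.25 | 6.0–9.0% |
| 20% | 0.25–0.50 | 9.0–21.6% |
| 30% | 0.38–0.75 | 14.2–42.0% |

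The effect runs from negligible to serious, and it depends on a quantity that the plan neither gives nor arranges to measure.

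**The case against.** The strongest reply is that nothing in the documents demonstrates a different average error. They give no error by arm and no towel counts, only different access. Different random error would add noise alone. This stands, and it limits the point to exposure to differential error.

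Second, the plan speaks of calculating the blood suctioned, not the canister volume, and this can be read as already net of irrigation. That is a fair reading. What is missing is the written step, so the irrigation part is closer to missing detail than to a faulty method. A reader might also infer that irrigation inflates only the laparoscopic figure. The documents do not support that: they do not say that irrigation is absent or smaller in open cases.

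Third, the 400 and 80 mL are worst-case figures on assumed values, with every towel wrong by the maximum in the same direction. That is correct, and they should be read only as showing how the error scales with towel count.

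Fourth, the consequence is limited. Blood loss is one of several secondary outcomes, it does not drive the sample size, Section 5 does not name it, and the Background statement is a summary of literature. This also stands.

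None of these replies supplies the missing volume per towel. A fixed wrong value would not average out, and it would cancel only if towel use were equal in the two arms or another error happened to offset it.

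**Conclusion.** The blood loss comparison is open to differential measurement error between arms, of unknown size and direction. The mechanism is an unstated volume per towel, applied by a team that knows the approach, in two arms that probably use towels to a different extent. On assumed values the towel component alone could differ between arms by anything from 0 mL (equal counts, or a correct volume per towel) to 320 mL (40 mL error, 10 versus 2 towels).

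A reader might go further and infer that the comparison is biased, or biased towards one approach. The documents do not support that. Bias needs a different average error in the two arms, and no section gives the error, the towel counts or the irrigation volumes. A fixed error per towel could push the open figure either way.

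This is a minor point about a secondary outcome. It is worth acting on because the remedy is cheap and the measurements cannot be recovered once the operation is over.

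**What to change.** In Section 6 (Methodology in details), replace the towel count with weighing: weigh towels and gauze dry and after use, and convert the gain to volume with one factor written in the protocol. Record the irrigation volume and state that it is subtracted from the suction volume. Use the same form in both arms.

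This removes the assumed volume per towel and the judgement of what counts as soaked. It changes measurement only, not care. It does not separate blood from other fluids such as ascites, so a residual error remains.

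The cost is a scale in theatre, extra entries on the theatre record, and a few minutes of nursing time per case over about 24 operations. The change needs to be in place before the first operation.

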## 6. Study Design:

Prospective comparative randomized clinical study

- **Study Methods**

- **Population of study:**

Patients presenting to KASR ALAINY hospital requiring pancreaticoduodenectomy

- **Study location:**

KASR ALAINY Hospitals – Cairo University

- **Inclusion criteria:**

- Patients presenting with pancreatic head tumours, cholangiocarcinoma, duodenal tumours (1st, 2nd and 3rd part) and ampullary tumours who are fit for either open or laparoscopic pancreaticoduodenectomy

- **Exclusion criteria:**

- Patients who are deemed inoperable due to the presence of metastases

- Patients with irresectable tumours

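### Leakage is a primary outcome with no case definition or counting window, and its confirmatory tests are left to discretion, so patients with no suspected leak need have no assay value

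*Combined protocol and SAP*

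**What the plan says.** The protocol's section 9 (Study outcomes) lists "Incidence of pancreatic and biliary leakage" under the primary outcome. No grade, threshold or time limit accompanies it. Section 11 (Statistical analysis) is a heading without text in the copy reviewed, so it adds no definition.

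Detection is described only in section 6, under the detailed methodology: "Daily serial abdominal examination to exclude or suspect pancreatic or biliary leakage will be done. Further laboratory assessment will be done if required". The tests meant include "serum and drain amylase, serum and drain bilirubin". On CT the plan says "imaging in the form of an abdomen and pelvis CT study may be done if required". It gives no trigger, sampling day or cut-off for any of these tests, and no last day for the daily examination.

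The design is described as "Prospective comparative randomized clinical study". Blinding of patients, ward staff or outcome assessors is not mentioned. The wounds differ: "Open approach will entail a roof top incision", while the laparoscopic approach uses several small ports. The plan adds "Daily wound assessment will be done starting 48 hours following surgery", without saying who does this. On numbers, section 10 states that "a minimum of 12 patients in each group were required".

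**The concern.** Two gaps meet on one primary outcome, and they rest on evidence of different strength.

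The first is plain from the text. Without a definition or window, two assessors could count the same patient differently and both follow the protocol. A reader could not tell whether a recorded leak was clinically evident or a laboratory finding, or up to which day it counted. If leakage is an assay finding, untested patients have no value. If it is a clinical event, it rests on an examination with no stated criteria.

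The second is an inference. The decision to test is discretionary, and those who take it can probably see which operation was done. Randomization balances patients at baseline but does not equalise later decisions to test. A difference in leak rates could then partly reflect how hard leaks were looked for.

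**Working it through.** **What the text establishes**

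| Element | In the plan | Not in the plan |
|---|---|---|
| Outcome (section 9) | Incidence of leakage, primary | Definition, grade, window |
| Check on every patient (section 6) | Daily abdominal examination | Criteria for calling a leak, last day |
| Amylase, bilirubin, CT (section 6) | Discretionary | Trigger, day, cut-off |
| Who sees the arm (section 6) | Different incisions, daily wound checks | Any blinding statement, any named assessor |

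The first three rows show the definition gap and the missing assay data directly. The last supports only an inference.

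**The plan's own figure**

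The plan gives no leak rate or detection rate. Its one calculation, 12 per group, concerns hospital stay. From the stated means and SDs, the difference is 8.9 − 4.7 = 4.2 days, the SD is √((1.125² + 5.425²)/2) = 3.918, and d = 4.2/3.918 = 1.072. A one-sided t test at 0.05 then needs 12 per group (power 81.6%); a two-sided test needs 15 (power 70.9% at 12). The figure is used below only as the number of patients; it says nothing about leakage.

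**Illustration of scale (all rates assumed)**

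Assume equal true leakage in both arms and no false positives. Then:

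spurious difference = true rate × (detection in arm A − detection in arm B)

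SE of the observed difference = √[(p₁(1 − p₁) + p₂(1 − p₂))/12], where p₁ and p₂ are the observed rates.

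| True rate | Detection A, B | Observed rates | Difference | Patients per 12 | SE | Difference/SE |
|---|---|---|---|---|---|---|
| 25% | 90%, 90% | 22.5%, 22.5% | 0 | 0 | 17.0 points | 0 |
| 25% | 90%, 60% | 22.5%, 15.0% | 7.5 points | 0.90 | 15.9 points | 0.47 |
| 35% | 90%, 60% | 31.5%, 21.0% | 10.5 points | 1.26 | 17.8 points | 0.59 |
| 30% | 90%, 50% | 27.0%, 15.0% | 12.0 points | 1.44 | 16.4 points | 0.73 |

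The last row shows that the ceiling depends on how low detection is allowed to fall. A and B are not assigned to either operation, because the plan gives no basis for a direction.

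**Effect on testing and precision**

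- An exact two-sided Fisher test at 0.05 with 12 per arm rejects with probability 2.0% at 22.5% v 15.0%, and 3.4% at 31.5% v 21.0%. Both are below the nominal 5%.
- With perfect detection and an assumed true 15% v 35%, the same test has 9.3% power.
- One reclassified patient moves an arm's rate by 1/12 = 8.3 points.

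Unequal detection at these values would distort the estimate more than it would produce false significance. The small sample limits this comparison more.

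**Assay count**

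Four assays per patient (amylase and bilirubin, each in serum and drain fluid) × 24 patients = 96 per scheduled day. Three days would be 96 × 3 = 288. Since 12 per group is a minimum, these counts rise with enrolment. They fall where a patient has no drain fluid.

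**The case against.** The strongest reply is that the testing rule is worded identically for both arms, and nothing in the plan shows that it would be applied differently. The plan does not say who examines the abdomen, inspects the wounds or orders tests. On assumed values the spurious gap stays below one standard error, and with 12 per arm the leak comparison is weak however leaks are found.

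All of this stands, and it limits the point. A reader might infer that the assessors are known to be unblinded, or that the leak comparison is biased. The documents support neither. They are silent on blinding, and visibility of the arm is inferred from that silence and from the different wounds.

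A reader might also conclude that the main comparison should rest on scheduled assays alone. That goes too far. The stated outcome is the incidence of leakage, and counting assays only would drop clinically evident leaks, including any after the last scheduled day.

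The reply does not touch the missing definition and window, or the lack of assay values in unsuspected patients. Those follow from the text whatever staff can see. Low power does not excuse them: leakage is a primary outcome, and readers must know what was counted.

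**Conclusion.** The point holds as a defect of definition and data collection, with a risk of unequal ascertainment attached. As written, the leakage outcome cannot be interpreted, and the absence of assay values in unsuspected patients cannot be repaired at analysis.

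The risk rests on two inferences: that those deciding on tests can see the arm, and that this could affect how often they test. Its size and direction cannot be derived from the documents. The illustration gives 0 to 7.5 points at 25% true leakage and up to 12 points among the other assumed combinations. It should not be read as an estimate of bias in this trial.

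The plan should be changed before patients are assessed, because the missing data cannot be obtained later. Confidence is medium. The absence of a definition is judged on the text reviewed, which lacks the front pages but includes the methodology, outcomes and sample size sections.

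**What to change.** - **Sampling.** For endpoint purposes, take the drain and serum amylase and bilirubin assays already listed on the same pre-set postoperative days in every patient in both arms.
- **Definition.** Classify leakage by one written definition and counting window, fixed in advance and applied identically to both arms. It should cover all leaks, including clinically evident ones, and state how patients without drain fluid are classified.
- **Reporting.** Give by arm how each leak was found (scheduled assay, clinical, or discretionary test or CT) and how many patients had each test. Add a comparison on scheduled assays only as a sensitivity analysis.

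The sponsor chooses the days, thresholds and window. Clinical work-up on suspicion stays at the clinicians' discretion.

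The cost is a definition paragraph and about 96 assays per scheduled day at the minimum of 24 patients, more if more are enrolled, in a trial that declares no funding. The recorded leak rate may change, and scheduled results may prompt further work-up. The change reduces the risk of unequal ascertainment without removing it, since whether drain fluid is available may itself depend on discretionary decisions. It does nothing for precision at 12 per arm.
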